1. To evaluate the toxicity profile of intraperitoneal talimogene laherparepvec in patients with peritoneal surface dissemination from gastrointestinal, fallopian tube, ovarian, or primary peritoneal tumors.

Secondary Objectives

1. To evaluate the pharmacokinetic profile and viral shedding of talimogene laherparepvec by measuring viral load in plasma and urine as well as viral load in peritoneal washings.

Exploratory Objectives

1. To evaluate the magnitude and duration of tumor response.
2. To evaluate the time to tumor progression as measured by radiographic imaging, clinical symptoms, and/or tumor marker levels.
3. To describe the clinical activity of talimogene laherparepvec, as measured by overall survival.
4. To evaluate the changes in peritoneal cavity leukocyte populations after the treatment of peritoneal surface dissemination of gastrointestinal, fallopian tube, ovarian or primary peritoneal cancers with talimogene laherparepvec.

Patient Population

Patients must have measurable stage IV peritoneal surface dissemination of gastrointestinal or ovarian cancer on radiographic imaging that cannot be completely resected at time of abdominal exploration or elevated CEA/CA-125 as markers of disease.

Study Design

This is a non-randomized, open-label Phase I trial in patients with Stage IV peritoneal surface dissemination from gastrointestinal, fallopian tube, ovarian, or primary peritoneal tumors enrolled at the University of Illinois College of Medicine at Chicago, Duke Cancer Institute, and select external collaborating institutions. All subjects will complete an extensive medical history, baseline physical examination and clinical assessment to ensure subject eligibility requirements (see Eligibility Criteria for details) within 4 weeks of starting study drug. All eligible patients must have a peritoneal catheter placed prior to the initiation of therapy.

There will be two stages, a Dose Escalation Cohort, and a Dose Expansion Cohort. All patients will receive an initial seroconversion dose of talimogene laherparepvec on Cycle 1 Day 1 to enable seroconversion as described in the currently approved treatment protocol for the treatment of cutaneous melanoma. Three weeks after the seroconversion dose, patients will receive talimogene laherparepvec at the dose level for the cohort in which they are enrolled. They will be treated every 2 weeks for up to 4 doses (in addition to the initial seroconversion

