For subjects who discontinue study treatment with no documented disease progression and no subsequent anti-cancer treatment, they will be followed every 12 weeks or as clinically indicated with tumor evaluations consisting of restaging scan with RECIST 1.1 evaluation and blood tumor markers, until disease progression or start of new anti-cancer therapy is documented

Correlative Studies

The association between biomarker expression and clinical outcomes will be explored with the following blood and tumor tissue specimen collections and specified time points from all subjects:

- *Tumor Tissue.* If available, archived FFPE tumor samples will be obtained from all subjects at the end of the study, upon PI request.
- *Viral Load.* Blood and urine will be collected at baseline (prior to seroconversion dose on Cycle 1 Day 1), Cycle 1, Day 8, Cycle 1 Day 15, prior to treatment on Cycle 1 Day 22, Cycle 1 Day 29, prior to treatment Cycle 2 Day 1, prior to treatment on Cycle 3 Day 1, prior to treatment on Cycle 4 Day 1, at disease progression or off treatment, and 30-day off treatment follow-up. Peritoneal fluid will be collected at baseline (prior to seroconversion dose on Cycle 1 Day 1), prior to treatment Cycle 2 Day 1, prior to treatment on Cycle 4 Day 1, at disease progression or off treatment, and 30-day off treatment follow-up
- *Peritoneal Cytokine Levels.* Collected at baseline (prior to seroconversion dose on Cycle 1 Day 1), prior to treatment on Cycle 2 Day 1, prior to treatment on Cycle 4 Day 1, and at disease progression or off treatment, and 30-day off treatment follow-up.
- *Immune Cells.* Immune cells from blood and peritoneal washings will be collected at baseline (prior to seroconversion dose on Cycle 1 Day 1), prior to treatment on Cycle 2 Day 1, prior to treatment on Cycle 4 Day 1, and at disease progression or off treatment, and 30-day off treatment follow-up.
- *Plasma.* Collected at baseline (prior to seroconversion dose on Cycle 1 Day 1), prior to treatment on Cycle 1 Day 22, prior to treatment on Cycle 2 Day 1, prior to treatment on Cycle

3 Day 1, prior to treatment on Cycle 4 Day 1, and at disease progression or off treatment, and 30-day off treatment follow-up.

- *Pharmacogenomics.* Subjects will have whole blood collected at baseline.

TABLE OF CONTENTS

PROTOCOL VERSIONS	2
SPONSOR CONTACT INFORMATION	3
PROTOCOL SYNOPSIS	4
TABLE OF CONTENTS	8
LIST OF ABBREVIATIONS	10
1.0 INTRODUCTION	11
1.1 Background	11
1.2 Study Drug	12

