2.2 Secondary Objectives

The secondary objective of this trial is:

1. To evaluate the pharmacokinetic profile and viral shedding of talimogene laherparepvec by measuring viral load in plasma and urine as well as viral load in peritoneal fluid.

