5.4 Follow-up Period

Subjects should return 30 (± 7) days after their last dose of study drug for an off-treatment visit to complete the following study procedures:

- Physical examination
- Abdominal measurement
- Vital signs and weight
- Concomitant medications
- ECOG performance status
- Adverse event assessment
- CBC with differential
- Chemistries including LFTs
- Serum pregnancy test (only for women of childbearing potential)
- Viral load (at disease progression and 30 day off treatment follow up)
- Peritoneal cytokines (at disease progression or off treatment, and 30 day off treatment follow up)
- Immune cells (at disease progression or off treatment, and 30 day off treatment follow up)
- Plasma (at disease progression or off treatment)

At the time of the follow up visit, the treating physician can determine whether or not to remove the IP catheter. If they anticipate using it for other IP therapies, it can be left in. If catheter is removed, treating physician may also determine whether it is clinically indicated to do PT/PTT. Additional follow-up may occur for subjects with adverse events (AEs) related to study drug that are ongoing at the time of this off-treatment visit unless AE is deemed unresolvable or subject has started a new anti-cancer treatment regimen.

For long-term follow up, subjects will be followed for progression every 12 weeks or as indicated until disease progression or start of new anti-cancer therapy. For subjects that complete or discontinue treatment without documented disease progression, subjects will have disease status (blood tumor marker(s) and restaging scans with RECIST 1.1 evaluation every 12 weeks) followed until disease progression or start of new anti-cancer treatment regimen.

All subjects will be followed for survival for up to 1 year after completing treatment. Survival status may be collected by personal interviews or review of medical records.

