8.2 Immune Cells

Peripheral blood and peritoneal washings will be collected for immune cells from each subject at the following timepoints: baseline (prior to seroconversion dose on C1D1), prior to treatment on C2D1, prior to treatment on C4D1, and 30-day off treatment follow-up. If the subject comes off treatment mid cycle, take an additional plasma sample at the time of disease progression or off treatment. Refer to *Study Manual* for collection and submission details.

Peritoneal immune cells will be processed and stored by the Duke Immune Profiling Core facility under the direction of [name]. Peripheral blood immune cells will be processed and stored by the Substrate Services Core and Research Support (SSCRS) laboratory. All samples will be transferred for analysis to [name] at LSU. Polychromatic flow cytometry (PFC) panels will be used to compare treatment related changes in both tumor and peripheral immune cell compartments. Up to 50 markers may be analyzed using 3 PFC panels: 1) a 12-color 'Exhaustion Panel', 2) a 12-color 'Tumor Reactive T Cell Panel', and 3) a 14-color regulatory T cell (Treg) and monocytic myeloid-derived suppressor cells (m-MDSC) panel. This analysis will be overseen by [name].

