8.5 Viral Load

Plasma and urine samples will be collected at the following time points: baseline (prior to seroconversion dose on C1D1), C1D8, C1D15, prior to treatment on C1D22, C1D29, prior to treatment on C2D1, prior

to treatment on C3D1, prior to treatment on C4D1, and at 30-day off treatment follow up visit. Peritoneal fluid will be collected at baseline (prior to seroconversion dose on C1D1), prior to treatment on C2D1, prior to treatment on C4D1, and 30-day off treatment follow-up. If the subject comes off treatment mid cycle, take an additional plasma and peritoneal sample at the time of disease progression or off treatment.

Plasma, urine and peritoneal fluid will be collected, frozen and stored at the site (at -80) until such time as deemed appropriate for analysis. When ready for viral load analysis, plasma, urine and peritoneal fluid samples will be shipped to [name] lab at LSU. A quantitative primer will be used to detect HSV-1 DNA in plasma, urine, and peritoneal fluid samples via polymerase chain reaction (PCR).

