9.1.4 Exploratory Endpoints

In addition to defining the MTD, the study will provide useful preliminary data concerning efficacy. Methods of assessing response will be specific to each individual patient as described in Section 5.6. In the subset of patients with radiographically measurable disease RECIST 1.1 criteria will be used.

Patients in the per protocol population will be classified as responder or non-responder and the proportion of patients exhibiting response at trial closure by any criteria will be estimated by the 90% confidence interval. Patients who experience a radiographic/tumor marker CR will undergo confirmatory laparoscopy.

Time to progression measured from study entry to documented progression of disease will be estimated by the method of Kaplan-Meier in the intent-to-treat population. Patients who withdraw from the trial prior to disease progression, are either lost to follow-up, die or begin alternative treatments prior to progression, will be censored at the date considered to be lost to follow-up, date of death, or the first day of alternative therapy.

For all efficacy endpoints, analyses will be performed overall and in the patients treated at the MTD. These analyses are primarily exploratory since the data will be from only a limited number of patients available for the study.

As a first approach to addressing our exploratory aim of evaluating changes in peritoneal cavity leukocyte populations after the treatment of peritoneal surface dissemination of gastrointestinal, fallopian tube, ovarian, and primary peritoneal cancers with talimogene laherparepvec, we will perform multi-color flow cytometry analysis on peritoneal lavage fluid from patients at baseline (prior to seroconversion dose on C1D1), prior to treatment on C2D1, and on C4D1. If the subject comes off treatment mid cycle, there will be an additional plasma sample at the time of disease progression or off treatment. Immune cells will be stained with fluorescent antibodies specific for markers of major leukocyte subsets as commonly performed by the [name] Lab.

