6. Must perform within 3-7 days prior to Cycle 1 Day 1 for patients with peritoneal port placed on study. Must be performed within 7 days prior to Cycle 1 Day 1 for patients with pre-existing peritoneal port. If completed within 7 days of Cycle 1 Day 1, no need to repeat.
7. Only for women of childbearing potential
8. After Cycle 1, may perform up to 3 days prior to Day 1.
9. Seroconversion dose of 4×10^6 PFU on Cycle 1 Day 1. Three weeks after initial seroconversion dose, talimogene laherparepvec administered at dose level every 2 weeks for up to 4 doses.
10. Radiographic assessments (i.e. restaging scans) include CT and/or MRI of chest, abdomen and pelvis after at least 8 weeks on study treatment. Same method for tumor assessment should be employed at every assessment.
11. Archived tumor will be collected at the end of the study, upon request from the PI, if FFPE tumor tissue is available. Refer to [Section] and Study Manual.
12. At baseline (prior to seroconversion dose on C1D1), C1D8, C1D15, prior to treatment on C1D22, C1D29, prior to treatment on C2D1, prior to treatment on C3D1, prior to treatment on C4D1, and 30-day off treatment follow up. If the subject comes off treatment mid cycle, take an additional plasma, urine, and peritoneal fluid samples at the time of disease progression or off treatment. *Note: C1D8, C1D15, C1D22, C1D29 and C3D1 timepoints are only for plasma and urine.
13. Peritoneal fluid for cytokines will be collected at baseline (prior to seroconversion dose on C1D1), prior to treatment on C2D1, prior to treatment on C4D1, and 30-day off treatment follow-up. If the subject comes off treatment mid cycle, take an additional peritoneal fluid sample at the time of disease progression or off treatment.
14. Peripheral blood and peritoneal washings collected at baseline (prior to seroconversion dose on C1D1), prior to treatment on C2D1, prior to treatment on C4D1, and 30-day off treatment follow-up. If the subject comes off treatment mid cycle, take an additional blood and peritoneal wash sample at the time of disease progression or off treatment.
15. At baseline (prior to seroconversion dose on C1D1), prior to treatment on C1D22 prior to treatment on C2D1, prior to treatment on C3D1, prior to treatment on C4D1, and 30-day off treatment follow-up. If the subject comes off treatment mid cycle, take an additional plasma sample at the time of disease progression or off treatment.

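### Sections 8.2 and 9.1.4 name plasma as the extra off-treatment sample for a flow-cytometry endpoint, and 9.1.4 leaves out the 30-day cell sample that the trial collects

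*Combined protocol and SAP*

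**What the plan says.** **Immune cells when a subject stops early.** Section 8.2 schedules peripheral blood and peritoneal washings at baseline, C2D1, C4D1 and the 30-day off-treatment visit, for analysis by flow cytometry. For early stopping it then says: "If the subject comes off treatment mid cycle, take an additional plasma sample at the time of disease progression or off treatment". Section 9.1.4, in the paragraph on the peritoneal leukocyte aim, plans flow cytometry on lavage fluid at baseline, C2D1 and C4D1 and adds that "there will be an additional plasma sample at the time of disease progression or off treatment".

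Three other places differ. Appendix C footnote 14 says "take an additional blood and peritoneal wash sample at the time of disease progression or off treatment". The synopsis (Correlative Studies) begins "Immune cells from blood and peritoneal washings will be collected at baseline" and goes on to list progression or off treatment and the 30-day visit. Section 5.4 lists "Immune cells (at disease progression or off treatment, and 30 day off treatment follow up".

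**Viral load.** For early stopping, section 8.5 says "take an additional plasma and peritoneal sample at the time of disease progression or off treatment", without urine. Appendix C footnote 12 asks for plasma, urine and peritoneal fluid, and the synopsis schedule also includes urine at that point. The secondary objective is "viral load in plasma and urine as well as viral load in peritoneal washings" in the synopsis and "viral load in plasma and urine as well as viral load in peritoneal fluid" in section 2.2.

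**The concern.** Plasma is the cell-free part of blood, so it cannot be stained for leukocyte markers. The section that defines the assay and the section that defines its analysis therefore both name a specimen that cannot yield the endpoint, at the one visit that exists to capture subjects who stop early. A sample not taken at progression cannot be taken later.

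The list of visits in 9.1.4 adds to this. The trial collects cells at the 30-day visit, but 9.1.4 does not list them. What is at stake is exploratory objective 4, the change in peritoneal leukocytes after treatment. If subjects who stop early supply fewer or no post-baseline cells, the description rests more heavily on those who tolerate treatment and do not progress.

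**Working it through.** The main check is a comparison of texts; no figure in the plan depends on this wording.

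**Step 1. Off-treatment specimen for immune cells, place by place.**

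| Place | Specimen at progression or off treatment | Usable for flow cytometry? |
|---|---|---|
| Section 8.2 | plasma | no |
| Section 9.1.4 | plasma | no |
| Appendix C, footnote 14 | blood and peritoneal wash | yes |
| Synopsis, Correlative Studies | blood and peritoneal washings | yes |
| Section 5.4 | immune cells | yes |

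The sentence in 8.2 also appears, word for word, in section 8.3 on plasma protein arrays, where it fits. It was probably carried over from there; that is an inference.

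**Step 2. Post-baseline cell samples per subject, by time of stopping.** The count assumes that the subject attends the 30-day visit, and applies the extra sample only to mid-cycle stopping, as footnote 14 does.

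| Subject stops | Footnote 14 | Section 8.2 taken literally | Visits listed in 9.1.4 |
|---|---|---|---|
| before C2D1 | off-treatment, 30-day = 2 | 30-day = 1 | 0 |
| after C2D1, before C4D1 | C2D1, off-treatment, 30-day = 3 | C2D1, 30-day = 2 | C2D1 = 1 |
| after C4D1, treatment completed | C2D1, C4D1, 30-day = 3 | C2D1, C4D1, 30-day = 3 | C2D1, C4D1 = 2 |

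Section 8.2 read literally costs an early stopper one cell sample, at off-treatment. The list in 9.1.4 costs an early stopper both remaining samples. A subject who stops before C2D1 then has nothing after baseline.

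**Step 3. Precision, for context.** Section 9.1.3 gives a 90% half-width of at most 0.237 with 12 patients for the cytokine proportion and says that immune markers will be handled similarly. That figure reproduces: 1.645 × √(0.25/12) = 0.237. The documents give no drop-out rate. If, as an assumption, 2, 3 or 4 of the 12 had no usable post-baseline cells, the half-width would be:

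- n = 10: 1.645 × √(0.25/10) = 0.260
- n = 9: 1.645 × √(0.25/9) = 0.274
- n = 8: 1.645 × √(0.25/8) = 0.291

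The loss of precision is small. Which subjects are missing matters more than how many.

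**Step 4. Peritoneal specimen by endpoint.** Immune cells come from washings, a wash or lavage in every place. Cytokines come from fluid in section 8.6 and footnote 13. Viral load comes from fluid in section 2.2, section 8.5, footnote 12 and the synopsis collection schedule; only the synopsis objective says washings.

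**The case against.** The strongest reply is that the right sample is already required in three places, including the study calendar, which sites are likely to work from. Section 8.2 itself keeps the 30-day blood and washings for every subject. Section 9.1.4 calls its paragraph a first approach, the aim is exploratory, and section 9.1.1 makes all analyses descriptive. Section 9.1.3 plans changes from baseline in immune markers without listing visits, so it does not shut out the 30-day cells. Collection details are left to a Study Manual that is not among the documents.

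Most of this stands, and it limits the size of the point. It does not remove the contradiction: a site that follows 8.2 literally may miss the off-treatment cells, and 9.1.4 does not list cells that the trial collects.

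A reader might infer two stronger things, and the documents support neither.

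- *Early stoppers lose all end-of-treatment cell data.* They do not. Footnote 14, the synopsis and section 5.4 require the cells, and 8.2 collects them at 30 days.
- *Peritoneal concentrations cannot be compared because washings and fluid are mixed.* Immune markers are percentages of cell subsets, which uniform dilution leaves unchanged. Within each endpoint the specimen name is consistent, apart from the synopsis objective for viral load. No passage assigns different specimens to different visits or subjects. Section 8.6 sends supernatant left over from cytokine work to viral-load testing, and the core that processes those samples also processes the peritoneal cells. This suggests one collection under several names, though that too is inference. The documents give no lavage or residual volume, so the size of any dilution effect cannot be worked out. Recording volumes would not by itself identify residual ascites, so a dilution-corrected analysis is not warranted on this evidence.

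**Conclusion.** Wrong as written; minor. Plasma in 8.2 and 9.1.4 cannot supply the flow-cytometry endpoint and contradicts footnote 14, the synopsis and section 5.4. Section 9.1.4 also omits the 30-day cells.

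The size is one cell sample at risk per early stopper if 8.2 is followed literally. If the visits in 9.1.4 are taken as the full list, a subject stopping before C2D1 adds no post-baseline cells and one stopping before C4D1 adds only C2D1, so objective 4 would lean towards subjects who remain on treatment. How many subjects this touches depends on a drop-out rate that the plan does not give.

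The missing urine in 8.5 and the washings/fluid difference in the secondary objective are smaller inconsistencies of the same kind. The primary safety objective is unaffected.

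**What to change.** 1. In 8.2 and 9.1.4, replace the off-treatment plasma sample with peripheral blood and a peritoneal wash, to match footnote 14.
2. State in 9.1.4 that the off-treatment and 30-day cell samples enter the leukocyte analysis.
3. In 8.5, add urine to the off-treatment viral-load samples, to match footnote 12 and the synopsis schedule.
4. Reconcile the synopsis secondary objective with section 2.2, section 8.5 and footnote 12, so that one term names the peritoneal viral-load specimen throughout.

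The cost is a wording amendment. No visit or sample is added beyond those already required by Appendix C.

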8.3 Protein Multiplex Arrays (Plasma)

Peripheral blood for plasma will be collected at baseline (prior to seroconversion dose on C1D1), prior to treatment on C1D22, prior to treatment on C2D1, prior to treatment on C3D1, prior to treatment on C4D1, and 30-day off treatment follow up. If the subject comes off treatment mid cycle, take an additional plasma sample at the time of disease progression or off treatment.

Refer to *Study Manual* for collection, processing, and submission details.

Plasma will be stored by the Duke Phase I Biomarker Laboratory under the direction of [name]. Aliquots will be retained from all samples for cytokine analysis by the the Duke Phase 1 Biomarker Laboratory. Remaining plasma samples will be transferred to the [name] Lab at LSU and markers of inflammation will be analyzed. Analyses will be performed on pre-treatment and on-treatment samples. Analyte levels, and changes in analyte levels, will be correlated with clinical outcome. Plasma and serum samples will be evaluated by ELISA for protein markers that may be associated with sensitivity or resistance to talimogene laherparepvec. These may include, but not limited to, IL1 β , IL2, IL4, IL5, IL6, sILR6R, sGP130, IL7, IL8, IL10, IL12, IL13, IL15, IL17A, IL17E, IL22, IL23, IFN γ , TGF β 1, and TGF β 2, but could include other markers that represent best science for this drug and involved signaling pathways.

